#### E. Seashore Rhythm Test (SSRT)‡

An assessment of auditory attention and concentration. This test evaluates an individuals ability to discriminate between non-verbal sounds. Administration time is 10 minutes. This assessment is not part of the TBI CDE, however it is a sensitive measure of attention in patients with TBI.

#### F. Test of Premorbid Functioning (ToPF)#:

An assessment that estimates an individual's pre-injury IQ and memory abilities and takes less than 10 minutes to complete. This is an update to the Wechsler Test of Adult Reading that is part of the TBI CDE. This test is only performed once at the baseline visit.

#### G. California Verbal Learning Test (CVLT-II)\*

A list-learning task to evaluate verbal learning/encoding, effects of interference, immediate and delayed recall, cued recall and delayed recognition. The CVLT-II takes approximately 20 minutes to administer.

#### H. Finger Tapping Test (FTT)‡

This is an assessment of motor speed to assist in motor lateralization. This task will take about 10 minutes to complete and is not part of the TBI CDE.

#### 4.4.4 Motor Assessments

CNS IRB Protocol Template (2.5.15)

These motor assessments# use specialized equipment that produces more detailed and likely more sensitive outcome measures than the recommended CDE for mobility and balance. Healthy volunteers will not perform this assessment.

#### A. Mobility assessment

Mobility will be assessed with the GAITRite System (CIR Systems Inc., Clifton, NJ, USA) to evaluate gait speed, stability and variability during various walking tasks as follows:

- 1. Free and fast walking: Walking will be evaluated along a hallway. Participants will be asked to walk across a 4.6 meter long electronic walkway (GAITRite) at their freely chosen speed and as fast as possible without running. This will be repeated each 2 times.
- 2. Performance during a dual task (DT) paradigm: This assessment will use a "walking while talking" paradigm. Subjects will be tested under 3 conditions:
  - i. Single task cognitive: e.g. generating words that start with the letter "s" and counting backwards by 3s starting at number 150 for 30 sec, while seated
  - ii. Single task gait: walking quietly across the electronic walkway at a comfortable speed. This is performed as described above.
  - iii. Dual tasking: walking at their comfortable speed and talking at the same time. Subjects will perform 2 trials: 1) e.g. walking across the walkway while generating words that start with the letter "f"; 2) e.g. walking across the walkway while counting backwards by 3 starting at number 148.
- 3. Reciprocal Coordination Test: this test will be done in the motion analysis lab. Reflective markers will be placed on the subjects' feet to record elliptical stepping performance during the freely chosen speed and a speed as fast as possible. The subject will grip the handrails and move the arms and legs smoothly in a forward elliptical motion. The subject will move at free and fast speeds for 20-30 seconds at each speed after an accommodation/warm up period of 1-2 minutes.

#### **B.** Balance assessment

Participants will perform the balance assessment using the Balance Master and SMART Balance Master System® (NeuroCom International, Inc; Clakamas, OR). Tests are performed on a long force plate and inside a booth, as described in Appendix 6. Center of gravity is measured during different tasks that are described below.

 The Limits of Stability (LOS) Test: This test is performed on the long force plate. Participants are required to actively shift their center of balance while standing (lean without taking a step) towards 8 targets that are presented individually. Targets are arranged in a circular pattern, and light up one by one. The system then computes changes in the person's center of gravity (COG) and outputs postural reaction time, movement velocity, excursion and directional control. During this test, subjects are in a comfortable standing position at the start and initiate all movements by themselves. One trial is collected for each target. They are encouraged to keep good posture and stay within their own postural limits but will have both standby assistance on the left side and a wall on their right for safety should they lose their balance. Outcome variables include reaction time, maximum and endpoint excursion and directionality.

- 2. Sensory Organization Test (SOT): This test is performed inside the booth. The task is to stand quietly under different conditions that challenge the 3 sensory systems involved in the control of balance: somatosensory, visual and vestibular systems. There are 6 conditions: 1) normal vision + fixed support surface, 2) no vision + fixed support surface, 3) vision sway (the booth moves with the movement of the subject's COG), 4) normal vision + surface sway (the surface moves with the movement of the subject's COG, 5) no vision + surface sway, 6) vision sway + surface sway. Three trials are collected for each condition. This test identifies how patients integrate normal and altered inputs from each system for the control of balance. The outcome variable measured in this test is called the equilibrium score. This score tells how well the patient's sway remains within the expected angular limits of stability (12.5 degrees) during each condition. Scores close to 100 indicate the patient was stable, there is very little sway. Scores that reach "0" indicate there was a fall.
- 3. Motor Control Tests (MCT): This test is performed inside the booth. The subject is instructed to maintain balance after sudden translations of the support surface. This test measures the latency of automatic postural response mediated by long loop pathways connecting the peripheral sensory and motor nerves to the brain. There are six conditions (translations):
  - i. Small forward
  - ii. Medium forward
  - iii. Large forward
  - iv. Small backward
  - v. Medium backward
  - vi. Large backward

Three trials are collected for each condition.

4. Adaptation Test (ADT): This test is performed inside the booth. The subject is instructed to maintain balance after repeated rotations of the support surface. This test measures the participant's ability to minimize sway over time when exposed to repeated perturbations in support surface. There are 2 conditions (rotations): toes up and toes down. Each condition is repeated 5 times in a row. This test reflects the patients' automatic ability to adapt to the perturbations by swaying less each time.

#### 4.4.5 Magnetic Resonance Imaging

Brain imaging\* is considered a TBI CDE and subjects must meet the criteria for MRI (repeated at each assessment time point). The MRI scans will be performed in the Department of Radiology in the NIH Clinical Center. Scanning will be performed on a 3 Tesla scanner. There will be no radiation exposure and no gadolinium will be administered. MRI scans may use research sequences that adhere to Specific Absorption Rate (SAR) safety guidelines and/or use research coils approved by the NMR Center Safety Committee. During the MRI, participants will be asked to lie on a table that can slide in and out of the cylinder. The MRI scan session will typically last 90 minutes and is unlikely to be more than 2 hours.

1. All women of childbearing potential will provide a urine sample for a pregnancy test performed no more than 24 hours before each MRI scan. Women who are discovered to be pregnant on their follow-up visit will no longer be eligible to participate in this study and will not perform any further imaging or study procedures.

2. A physician's order for a research brain MRI will be written in the subject's medical chart or entered into the electronic medical record by a member of the research team with clinical privileges as per study site policy. The research coordinator or assistant will escort the participant to the MR scanner in the CNRM Neuroimaging Core, housed at the NIH Clinical Center and will be in attendance with the participant throughout the procedure.

3. Subjects will be screened for MRI safety using the Screening Questionnaire used by the Radiology and Imaging Sciences Program of the Clinical Center (Appendix 4).

4. Subjects may be asked to lie still for up to 12 minutes at a time. While in the scanner they will hear loud knocking noises, and they will be fitted with earplugs or headphones to muffle the sound. They will be able to communicate with the MRI staff at all times during their scan, and they may ask to be moved out of the machine at any time.

5. Participants will first have a structural MRI scan. The structural MRI sequences we will use do not require contrast. They are not required to do any tasks during the structural MRI. Sequences used for the structural MRI may include T1 Magnetization Prepared Rapid Gradient Echo (MPRAGE), Fluid Attenuated Inversion Recovery (FLAIR), Diffusion Tensor Imaging (DTI), resting state functional connectivity (rfMRI), diffusion weighted imaging (DWI), Arterial Spin Labeling (ASL) to assess resting CBF, gradient echo (GRE) and/or T2\* susceptibility weighted imaging (SWI). If image quality of a given sequence is inadequate due to patient motion for example, these may be repeated at the discretion of the MRI technologist or radiologist. The structural scan takes approximately 45 minutes.

6. For the fMRI, the following cognitive test will be administered:

**Paced Auditory Serial Addition Test (PASAT)**: a measure of cognitive function that specifically assesses auditory information processing speed and flexibility, calculation ability, and working memory. Single digits are presented every 3 seconds and the patient must add each new digit to the one immediately prior to it. The PASAT takes approximately 10-15 minutes to complete.

7. The BOLD sequence with hypercapnia challenge will have a BOLD MRI scan with cerebral vascular reactivity (CVR) hypercapnia measurements. Region-specific CVR will be assessed using hypercapnia induced by breathing 5% carbon dioxide (CO2) mixed with 21%  $O_2$  and 74%  $N_2$ . Study participants will be taken out of the scanner and fitted with a breathing mask that covers the mouth or a mouthpiece and nose clip to keep the patient from breathing through his/her nose. After the mask or mouthpiece

and nose clip is in place, the patient is placed back into the magnet. Hypercapnia will be induced via a Douglas bag fitted with a valve to switch between room air and 5%  $CO_2$ 

All or parts of the planned MRI procedures may be omitted for participants with nonferromagnetic metal or other substances in the head that do not constitute a safety hazard but may create an artifact that will interfere with analysis. We may evaluate the quality of previous MRIs on the participant if available or consult a radiologist to help in making this determination.

All MRI scans will be performed with dedicated radiofrequency coils that have received approval from the FDA or the NIH NMR Center Safety Committee. Research MRI coils that are not approved by the FDA may be used in this study. The NMR Center Safety Committee will approve all research coils for human use. A list of research MRI coils used will be submitted to the IRB at the time of continuing review. The CNS IRB has previously determined that research coils approved by the NMR Center Safety Committee are non-significant-risk devices and that no Investigational Device Exemption is needed.

The IRB has determined that the 32-channel head coil that may be used in this study does not meet the definition of significant risk (SR) device in accordance with FDA regulations (21 CFR 812), and therefore is considered an NSR device.

A SR device means an investigational device that:

- Is intended as an implant and presents a potential for serious risk to the health, safety, or welfare of a subject;
- Is purported or represented to be for a use in supporting or sustaining human life and presents a potential for serious risk to the health, safety, or welfare of a subject;
- Is for a use of substantial importance in diagnosing, curing, mitigating, or treating disease, or otherwise preventing impairment of human health and presents a potential for serious risk to the health, safety, or welfare of a subject; or
- Otherwise presents a potential for serious risk to the health, safety, or welfare of a subject. (21 CFR 812.3(m))

#### 4.4.6 Physical Fitness Assessment

These physical fitness assessments use specialized equipment that produces more detailed and likely more sensitive outcome measures than the recommended CDE for physical function. Patients will perform a cardiopulmonary exercise tolerance test on the treadmill with measures of pulmonary gas exchange to determine their maximal exercise tolerance. Healthy volunteers will not perform this assessment.

#### A. Cardiopulmonary exercise test (CPET) and EKG#

A computerized treadmill with motor-driven speed and grade adjustments will be used for the graded exercise test. The treadmill was chosen as the method of testing because it is well known to evoke higher values of  $O_2$  consumption (VO2) at maximum exercise, compared to other standard methods such as the leg cycle ergometer. Also, treadmill walking is a functional performance measure and the RMD exercise laboratory personnel are well experienced in clinical treadmill exercise testing.

Subject preparation will consist of placing 10 electrodes on the chest at rest in the Mason-Likar 12-lead EKG modification for treadmill testing. The purpose of the EKG during the exercise test is to obtain digital HR information over the course of the CPET. After the electrodes have been placed, either a facemask placed over the lower portion of the subject's face (mouth and nose) or a mouthpiece and nose-clip will house the subject interface for pulmonary gas exchange. After collection of seated and standing resting data, the subject will begin the treadmill test. The test protocol begins with subjects walking at a slow speed on a flat treadmill. The speed and grade will then gradually increase at a rate that is supposed to bring the subject to exertional intolerance within 8 to 12 minutes. The target endpoint is exertional intolerance defined as the subjects expressed desire to stop walking despite strong verbal encouragement from the testing staff. A standard approach will be used to gain feedback from the subject regarding their current state of exhaustion during the test by frequently asking how they feel during the test. When they indicate they are becoming fatigued, the testing staff asks if they can continue for another minute. If the answer is "yes," after 30-45 additional seconds the subject is again asked if they can continue for an additional minute. If the answer is "yes," the process is repeated. When the subject's answer is "no," the subject is asked if they can continue for another 30 seconds. If the answer is "yes," then after an additional 15 seconds the subject is again asked if they can continue for an additional 30 seconds. If the answer is "yes," the process continues. When the answer is "no" or when the answer is "I must stop now," the test is stopped and the treadmill speed and grade are decreased to cool down levels. The test may also be stopped immediately at the subject's request, therefore the subject determines the stopping point and is never pushed beyond their expressed ability to continue. No expressed disappointment is ever mentioned to the subject in an attempt to force continuation. It is recognized that this stopping point is subjective and may occur at a level that is potentially lower than their actual metabolic capacity. To determine if the metabolic capacity has been reached there are two physiologic indices used. One is the attainment of 90% of the subjects maximum predicted heart rate (220 beats per minute minus one beat per minute per year of life). The other is attainment of an expiratory exchange ratio (total body oxygen consumption / carbon dioxide expiration) of 1.10 or greater as measured by pulmonary gas exchange analysis. One of these criteria must be met to substantiate attainment of maximal cardiorespiratory capacity.

#### **B.** Pulmonary gas exchange

Pulmonary gas analyses will be performed using a computerized metabolic cart including rapid response oxygen and carbon dioxide analyzers, and a pneumotachometer interfaced with a microprocessor. Subjects will interface the system using a fitted facemask or mouthpiece and nose-clip attached to a plastic air collection pneumotachometer. The pneumotachometer is in turn attached to a plastic tube connected to a flow pump, which regulates the volume of air passing into the oxygen and carbon dioxide analyzers. The total volume of air expired and inspired (passing through the plastic tube) is measured by a digital, bidirectional pneumotachometer. Gas exchange variables measured during the tests will be measured continuously, breath-by-breath. The main variable of interest obtained from pulmonary gas analyses is  $VO_2$ .  $VO_2$  will be determined electronically by the Haldane equation for every breath and the highest value recorded at volitional exhaustion will be recorded as the score for the measurement. Other pulmonary gas exchange variables (such as anaerobic threshold) may be analyzed to assist in explaining subjects' exercise response. These supporting variables will not require further data collection.

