# 11-CC-0088: Effect of aerobic exercise training on cardiorespiratory function in patients with TBI

In this study, results from 10 subjects (age,  $33 \pm 7$  years; mean  $\pm$  SD) suggest that patients with TBI are able to demonstrate improvements in cardiorespiratory function with a training regimen that is generally prescribed to the general population. Specifically, patients increased their time to volitional fatigue, attained higher peak O2 consumption and demonstrated improved aerobic capacity (Table 1). Patients exercised on a treadmill for 30 minutes at an intensity considered to be "vigorous" (i.e., heart rate range of 70 - 80 % heart rate reserve), 3 times a week for 12 weeks. Despite the challenging training regimen, patients were able to adhere and maintain their target intensity throughout the session duration (Table 2). These findings have been published and are available ahead of print [31].

CPET Variables	Pre	Post	$\Delta$	P-Value
Time to peak $VO_2(s)$	982 (113)	1066 (142)	+84 (45)	< 0.001
Peak VO 2 (ml/kg/min)	37.1 (8.2)	40.2 (8.1)	+3.1 (2.4)	0.003
Peak WR (W)	324 (90)	383 (104)	+59 (48)	0.005
Time at AT (s)	556 (92)	662 (92)	+106 (63)	< 0.001
VO 2 at AT (ml/kg/min)	18.9 (4.1)	22.5 (3.5)	+3.6 (2.1)	< 0.001

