### 8.2 Secondary Outcomes

Secondary outcome measures included here are those which have been shown previously or that we hypothesize to improve as results of exercise. Analysis will include comparisons of both exercise groups both combined and separately to the control group, and pre- to post-intervention changes within and across exercise groups in the following:

• Changes in other measures of cognitive function as measured by the

neuropsychological assessments

- Changes in motor assessments including balance and reaction time to perturbations
- Changes in cardiorespiratory fitness as measured by peak VO2 achieved and time on the treadmill
- Change in fatigue severity as measured in the FSS; other quality of life, physical activity, and sleep quality scales will be used to enhance interpretation of the FSS findings
- Changes in MRI findings, both structural and functional measures; e.g., increases in hippocampal brain volume, or increases in the degree of functional connectivity or fractional anisotropy between brain regions that sub serve motor, cognitive and behavioral functioning.
- Changes in biomarkers

We are also interested in examining relationships among various outcomes (functional, behavioral, structural, mechanistic, etc.) in persons with TBI. Therefore, secondary analyses may include correlations or comparisons of baseline measures within and across the groups. Comparisons of outcome measures including blood biomarkers, brain imaging, neuropsychological and questionnaire data will also be made to a reference healthy volunteer sample that is matched for sex and age within 5 years.

Table 4.	Summary	of t	the	Relevant	Outcome	Variables	for	the	Secondary	Outcome
Measures										

Test/Construct Measured	Relevant outcome variable
Gait Speed	Free and fast walking velocity
Dual Task Performance	Cognitive and motor cost (difference between DT and ST performance)
LOS/Dynamic Balance	Reaction time, maximal excursion
Elliptical Speed (reciprocal coordination)	Free and fast cadence on the elliptical
SOT/3 sensory systems	Equilibrium score for each sensory system
MCT/involuntary reaction time	Mean latency of responses
Adaptation/stability when perturbed	Sway velocity in 2 conditions

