# 9. Statistical Analysis

### 9.1 Analysis of data

The primary analysis is a mixed model (with time as the within-subject factor and exercise group as the between subject factor) analysis of variance (ANOVA) which will be used to determine significant differences in the primary (ANOVA) and secondary outcome variables (MANOVA by outcome category – i.e. motor, cognitive, behavioral, etc – to help control for multiple comparisons) as a result of exercise. Therefore, the data will include the time points immediately pre and post exercise for all subjects. We are interested in both main effects for time and exercise as well as potential interaction effects between exercise group and time.

All subjects completing the protocol and not withdrawing or presenting off study criteria will be included in the analyses. Secondary analyses related to protocol adherence and other aspects of feasibility are anticipated. Estimation of the necessary and sufficient sample size was calculated for a large effect change in the main outcome variable, pre- to post-training change in executive functioning. Significance will be set at p < 0.05.

While we do not anticipate that subjects will improve over time in the absence of exercise, we have included a waitlist control to evaluate this, and we will compare the amount of change over time in the control group versus the exercise group that were not waitlisted using an independent t-test. Also for the exercise group that was not waitlisted, there will be a three month follow up period evaluated to determine whether there is any change compared to the end of the exercise period using paired t-tests.

The change in aerobic capacity and fast elliptical speed will be correlated with changes in the other outcomes measures. Baseline dopamine transmission scores will also be correlated with all motor outcomes using linear regression.

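### Peak VO2 is scored as the highest breath with no averaging window, which overstates the absolute peak and adds avoidable noise to a secondary outcome

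*Combined protocol and SAP*

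**What the plan says.** Section 4.4.6 B of the protocol describes the gas exchange measurement: "Gas exchange variables measured during the tests will be measured continuously, breath-by-breath". VO2 is computed for each breath, and "the highest value recorded at volitional exhaustion will be recorded as the score for the measurement". Read literally, the score is one breath, the largest. No section states an averaging window, a smoothing step or a rule for artefact breaths.

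Section 8.2 lists the secondary outcome as "Changes in cardiorespiratory fitness as measured by peak" VO2, paired with treadmill time. The physical performance table in the same section adds VO2 at peak exercise without saying how it is derived. Section 9.1 then plans a further use: "The change in aerobic capacity and fast elliptical speed will be correlated with changes in the other outcomes measures". It does not say that aerobic capacity means peak VO2, although that is the natural reading.

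**The concern.** The largest of several noisy readings lies above the true level on average, and more so when there are more readings or each one is noisier. It also varies more from test to test than a mean of neighbouring breaths. One cough or one badly integrated breath can set a participant's score.

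Three uses of the score could suffer. Absolute peak values would read too high. The comparison of change between the exercise and waitlist groups would lose some power. If aerobic capacity in section 9.1 means peak VO2, the correlations with the other changes would be pulled toward zero. Every breath is already recorded, so the loss is avoidable.

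**Working it through.** **1. The plan's own figure.** The only precision information on peak VO2 is the pilot result in Table 1 (11-CC-0088, "results from 10 subjects"): before 37.1 (8.2), after 40.2 (8.1), change +3.1 (SD 2.4) ml/kg/min, p = 0.003. A paired t-test gives t = 3.1/(2.4/√10) = 4.08 on 9 df, two-sided p = 0.0027. The figure reproduces. The documents do not say how the pilot peak was scored.

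**2. Inputs.**
- From the documents: peak level 37.1; pilot change 3.1 (SD 2.4); a ramp meant to "bring the subject to exertional intolerance within 8 to 12 minutes" (section 4.4.6 A); 20 completers per group (section 9.2); "Significance will be set at p < 0.05" (section 9.1), taken as two-sided.
- Assumed, because the documents give no values: breath CV 3, 5 or 10% of 37.1 (SD 1.11, 1.86, 3.71); 40 breaths per minute; correlation between successive breaths 0 to 0.6; VO2 rising 2.5 ml/kg/min per minute over the last 2 minutes; SD of true change between people 2.0.

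**3. Level and noise of the score.** The last 2 minutes of the ramp were simulated (20,000 tests per setting). Two scores were compared: the single highest breath and the highest rolling 30 s mean (20 breaths).

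Bias against the true peak was +1.4 to +7.2 ml/kg/min for the single breath and -0.6 to +0.3 for the 30 s mean.

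**4. Change score and power.** SD of change = √(2.0² + 2 × SD of score²). For CV 10% and independent breaths this is √(4 + 2 × 1.71²) = 3.14 for the single breath and √(4 + 2 × 0.72²) = 2.24 for the 30 s mean. Power is for a two-sample t-test at 20 per arm and a difference of 3.1, from the noncentral t with 38 df and noncentrality 3.1/(SD × √(2/20)). It stands in for the planned ANOVA and MANOVA. In each cell the single breath comes first and the 30 s mean second; ratios use unrounded values.

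| CV | Correlation | SD of score | Ratio | SD of change | Ratio | Power at 3.1 |
|---|---|---|---|---|---|---|
| 3% | 0 | 0.59 / 0.24 | 2.4 | 2.17 / 2.03 | 1.07 | 99.3% / 99.7% |
| 3% | 0.6 | 0.69 / 0.45 | 1.5 | 2.22 / 2.10 | 1.06 | 99.0% / 99.5% |
| 5% | 0 | 0.92 / 0.39 | 2.3 | 2.38 / 2.08 | 1.15 | 98.0% / 99.6% |
| 5% | 0.6 | 1.06 / 0.70 | 1.5 | 2.50 / 2.23 | 1.12 | 96.9% / 99.0% |
| 10% | 0 | 1.71 / 0.72 | 2.4 | 3.14 / 2.24 | 1.40 | 86.0% / 98.9% |
| 10% | 0.6 | 1.93 / 1.26 | 1.5 | 3.39 / 2.68 | 1.27 | 80.5% / 94.6% |

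**5. Anchoring on the pilot SD instead of the assumed 2.0.** This uses a highest 20 s mean, independent breaths and 40 breaths per minute.
- If 2.4 came from averaged data, single-breath scoring raises it to √(2.4² + 2 × (single SD² - mean SD²)). That gives 2.58 at breath SD 1.5 and 3.22 at breath SD 3.7 (ratio 1.07 to 1.34).
- If 2.4 came from single breaths, averaging lowers it to 2.21 at breath SD 1.5 and 1.61 at breath SD 3.0 (ratio 1.09 to 1.49).
- In the second case CV 10% does not fit: breath noise alone would give √2 × 1.71 = 2.42, already above the whole observed 2.4.

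**6. Correlations.** Noise multiplies a true correlation by 2.0/SD of change. From the table this is 2.0/2.50 = 0.80 to 2.0/2.17 = 0.92 for the single breath at CV 3 to 5%, against 2.0/2.23 = 0.90 to 2.0/2.03 = 0.99 for the 30 s mean. At CV 10% it is 0.59 to 0.64 against 0.75 to 0.89.

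**7. Does the bias differ between visits?** If breathing near exhaustion rises from 40 to 45 breaths per minute after training, the bias of the single-breath score shifts by 0.10 (breath SD 2.2) to 0.16 (breath SD 3.7) ml/kg/min. That is small against 3.1.

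**The case against.** The defence has four good arguments.

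- **The bias mostly cancels.** The same rule applies in every arm and at every visit, and step 7 shows how little a change in breathing rate matters. This stands, unless breath variability itself changes with training. A reader might infer that the training effect will be overstated; the documents do not support that.
- **The noise penalty on the outcome is modest.** A reader might infer that peak VO2 is about twice as noisy as it need be. That describes breath noise alone, with near-independent breaths. The trial analyses change, which also carries true differences between people, and there the ratio is about 1.1 to 1.5.
- **A large power loss needs favourable assumptions.** One can pick a smaller difference, such as 2.0 ml/kg/min, and a CV of 10% and obtain a steep fall. The documents name no such difference, and CV 10% conflicts with the pilot SD if the pilot used single breaths. At 3.1 and CV 3 to 5% little is lost. The 3.1 is itself an uncontrolled pre-post change, so it is only indicative.
- **Peak VO2 is one of several fitness measures.** Treadmill time, peak work rate and VO2 at the anaerobic threshold are also listed.

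The cart may also export averaged values, but the protocol does not say so, and the window would still be undefined. It could be objected too that a highest interval mean is itself a maximum. Step 3 tests that rule directly: it had less noise and less bias than the single breath in every setting. The objections limit the size of the problem; they do not remove it.

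**Conclusion.** The point holds with limited size. As written, the rule makes peak VO2 a single-breath maximum. The absolute peak is overstated, and a secondary outcome carries noise that averaging recorded breaths would reduce. The section 9.1 correlations are affected too if aerobic capacity there means peak VO2.

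Under the stated assumptions the breath-noise SD is about 1.5 to 2.4 times that of a highest 30 s mean, and the SD of change about 1.1 to 1.5 times larger. For a difference of 3.1 ml/kg/min, power is about 97 to 99% against 99% or more at CV 3 to 5%, and about 81 to 86% against 95 to 99% at CV 10%. The last case is plausible only if the pilot SD of 2.4 came from averaged data. These sizes rest on breath variability and correlation that the documents do not give.

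A reader might also infer that the trial's main result is at risk. It is not: the primary outcome is Trail Making Test Part B, and the section 9.2 sample size rests on that test.

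**What to change.** In section 4.4.6 B, define peak VO2 as the highest fixed-interval average, for example 30 s, near the end of the exercise test. State whether the window is rolling or in consecutive blocks, and compute it identically at all visits. In section 9.1, say whether change in aerobic capacity means change in this measure.

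The cost is a sentence or two and a cart or post-processing setting. No new data, visits or participant burden are needed, and completed tests can be rescored if the breath files were kept. The downside is slightly lower absolute values, and less comparability with the pilot if its peaks were scored by single breath.
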